11.4 Healthcare resource utilization, including hospitalization

The following summaries will be produced using descriptive statistics by entire study, study cycle, actual dose level received within study cycle and RLZ total using the SS:

- Number of study participants with hospitalization/ emergency room (ER) visit
- Total number of hospitalization/ ER visit
- Reason of hospitalization/ ER visit
- Number of study participants discharged from hospitalization/ ER visit
- Total number of days in hospitalization/ ER visit

Note:

- Total number of days in hospitalization/ ER visit for each hospitalization/ER visit= Discharge date – hospitalization/ ER visit date +1
- Total number of days in hospitalization/ ER visit for each cycle = sum of total number of days in hospitalization/ ER visit for all hospitalization/ER visit within the cycle
- Total number of days in hospitalization/ ER visit during study = sum of total number of days in hospitalization/ ER visit for all cycles
- Only hospitalization started after first IMP and before last visit will be considered in the summary
- In case of completely missing discharge date, the following imputation rules will be applied for the discharge date:
 - Hospital start date of next hospital stay – 1 as end date of this hospital stay;
 - Death date in case participant died and the end date of hospital stay is missing;
 - Last visit date if the end date of hospital stay is missing and the participant did not die.
- In case that discharge date is partially missing (day missing) then impute to last day of the month unless this date is after the hospital start date of a next stay (then impute to 1 day before) or it becomes after death date (then impute to death date).

A listing will be provided for the hospitalization/ ER visit. The data from Health Care Provider Consultations Not Foreseen by the Protocol CRF form will also be listed.

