2.2.5 Immunological endpoints

- Change from Baseline (Day 1)^b in [REDACTED] in participants experiencing infusion reactions

For initial fixed treatment cycle only:

- Change from Baseline (Day 1) in serum Ig concentrations [REDACTED] at each scheduled assessment during Treatment and Observation Periods

Note:

^b Baseline will be used from the sample collected at Day 1 (Visit 2) in MG0003. Other exploratory safety biomarkers may be assessed.

2.2.6 **Rescue therapy and healthcare endpoints**

- Use of rescue therapy (yes/no)
- Time to rescue therapy
- Healthcare resource utilization, including hospitalization (type: intensive care unit [ICU]/non-ICU and duration in each respective type of care)

2.2.7 **COVID-19 related endpoint**

- [REDACTED]

2.3 **Study design and conduct**

[figure not shown]
2.3.1 **Overall design**

This is a Phase 3, multicenter, 2-arm, OLE study to evaluate 6-week treatment cycles of rozanolixizumab in study participants with gMG. MG0007 is an extension study of MG0003. The study is open to study participants from MG0003 and MG0004.

Eligible study participants from MG0003 will be randomized to receive an initial fixed 6-week treatment cycle of a subcutaneous dose of rozanolixizumab equivalent to approximately 7mg/kg or 10mg/kg weekly (QW) (see [Figure 2–1](#) and [Figure 2–2](#)), followed by an Observation Period that begins after the last dose of that treatment cycle as per assessments described in the Schedule of Activities in protocol.

Eligible study participants from MG0004 who have completed at least 6 scheduled visits for rozanolixizumab treatment and the Premature End of Treatment (PEOT) visit can move directly into the Observation Period in MG0007. Additionally, eligible study participants from MG0004 who are in the Observation Period can complete the End of Study (EOS) visit and move directly into the Observation Period in MG0007 (see [Figure 2–1](#) and [Figure 2–2](#)). If IMP treatment was withheld for low IgG in MG0004, study participant's missed dose(s) can be counted as part of the total 6 visits for completion of MG0004 and meet eligibility requirements for MG0007. These study participants will undergo their first MG0007 treatment with rozanolixizumab upon worsening of gMG symptoms. Participants will continue on their last treatment dose from MG0004. Dose adjustments may be applied in future cycles as per description below.

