- If only the year is specified, then use December 31 of the known year. If an imputed stop date is after last contact date and last contact date is before the data cutoff date, then assign last contact date as the stop date. If an imputed stop date is after last contact date and last contact date is after the data cutoff date, then assign data cut-off date as the stop date.
- If the stop date is completely unknown, then use discharge date or data cut-off date. Discharge date refers to the date of the end of study visit for completed participants or the date of discontinuation for participants that were withdrawn. For any AEs with known start date after the date of discontinuation, the date of last contact will be used as the discharge date. For participants still ongoing in the study at the time of the data cut-off, and for whom no discharge date is available, the date of the data cut-off will be used instead of the discharge date.

Any medication with a start date on the first dosing date and time unknown, will be assumed to be concomitant.

Imputed AE dates will be used for the calculation of duration of AEs as described in [Table 4–1](#).

Table 4–1: Calculation rules for duration of AEs

Data availability	Onset date	Outcome date	Calculation rules
Complete data	D1	D2	$\text{Duration} = D2 - D1 + 1 \text{ d}$
Start date partially or completely missing	--	D2	$\text{Duration} \leq D2 - D0 + 1 \text{ d}$ Notes: D0 is imputed start date per above rules.
End date partially or completely missing	D1	--	For ongoing AE: $\text{Duration} \geq D3 - D1 \text{ d}$ For resolved AE: $\text{Duration} \leq D3 - D1 \text{ d}$ Notes: D3 is imputed end date per above rules.
Start and end date partially or completely missing	--	--	For ongoing AE: $\text{Duration} \geq D3 - D0 \text{ d}$ For resolved AE: $\text{Duration} \leq D3 - D0 \text{ d}$ Notes: D0 is imputed start date and D3 is imputed end date per above rules.

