8.1 Extent of exposure

The following dosing information for entire study will be summarized using SS by RLZ total:

- Number of participants receiving 7mg/kg or 10mg/kg initially and the treatment sequence (eg 7mg/kg-7mg/kg, 7mg/kg-10mg/kg, etc.)

The following dosing information for entire study will be summarized using SS by the first cycle treatment and RLZ total:

- Total number of study cycles (regardless of the first cycle being mandatory or not) as a continuous variable (n, sum, mean, sd, median, min, max will be provided)
- Number of study cycles (1, 2, 3, ..., until the maximum number of study cycles)
- Number of cycles per participant year rate
- Time in study [<3 months (90 days), >=3 to <6 months (180 days), >=6 to <9 months (270 days), >=9 to <12 months (360 days), >=12 to <24 months (720 days), >=24 months to <30 months (900 days), >=30 to <36 months (1080 days), >=36 months (1080 days)]
- Time in study (months) and time in study (days) as continuous variables (n, sum, mean, sd, median, min, max will be provided)

Note:

- Time in study=Date of last visit or withdrawal–Date of first visit+1. Time in study last category will be adjusted based on data to have non-zero count in last category.
- Number of cycles per participant year rate=(Sum of number of cycles)/(Sum of participant year), where Participant year=Time in study /365.25.
- 1 month=30 days.

The following dosing information will be summarized using SS by entire study, study cycle, actual dose received within each cycle and RLZ total:

- Number of infusions received as a continuous variable (n, sum, mean, sd, median, min, max will be provided)
- Number of infusions received by the following categories:
 - For each study cycle: 1, 2, 3, 4, 5, 6
 - For entire study: 1-6, 7-12, 13-18, 19-24, 25-30, 31-36, 37-42, 43-48, ..., until last interval where the maximum number of infusions falls into.

Notes:

- Values for entire study will be the summation from study cycles;

A figure for actual dose received in all study cycles by participant will be provided. Figures of exposure by time, by number of cycles, by drug free time for participants from MG0004, and by drug free time for participants from MG0003 will also be provided.

All IMP administration details will be listed.

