11.3 Time to first rescue therapy

Time to first rescue therapy (in days) is defined as: Date of first post-baseline rescue therapy use - Date of first IMP in the study + 1.

For participants who do not take rescue therapy, discontinued participants will be censored at their discontinuation date and completers will be censored at their last visit date.

The survival estimates of 1, 29, 43, 71, 99, 127, 155, 180, 300, 400, 500, 600, 700, 800, 900, and 1000 days to rescue therapy and the median times (with 95% CI) to rescue therapy will be

calculated using Kaplan-Meier method by initial RLZ dose level and RLZ total. Number of censored participants will be reported as well.

The median times to rescue therapy by study cycle will be calculated using Kaplan-Meier method for RLZ dose level received within study cycle and RLZ total. 95% CI of median times will be reported as well.

The time to rescue therapy will be listed using FAS.

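### The SAP 11.4 hospitalisation summary leaves out a terminal stay when no study visit follows the admission, mainly in participants who die

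*SAP*

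**What the plan says.** SAP 2.2.6 lists the endpoint as "Healthcare resource utilization, including hospitalization (type: intensive care unit [ICU]/non-ICU and duration in each respective type of care". Protocol Section 3 places it among the 'other' endpoints. SAP 11.4 summarises participants hospitalised or seen in an emergency room, numbers of such events, reasons, participants discharged, and total days, each on the Safety Set.

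Three rules in SAP 11.4 bear on the point:

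- The window: "Only hospitalization started after first IMP and before last visit will be considered in the summary". Last visit is not defined in that section.
- A completely missing discharge date in a fatal case: "Death date in case participant died and the end date of hospital stay is missing".
- A completely missing discharge date in a non-fatal case: "Last visit date if the end date of hospital stay is missing and the participant did not die".

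The section also says: "A listing will be provided for the hospitalization/ ER visit". The window is worded for the summary only.

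Elsewhere the SAP does not always stop at the last visit. SAP 11.3, on time to first rescue therapy, says that "discontinued participants will be censored at their discontinuation date and completers will be censored at their last visit date". SAP 8.1 gives "Time in study=Date of last visit or withdrawal" as the end date for exposure time. SAP 4.2.2, on unknown stop dates, says: "For any AEs with known start date after the date of discontinuation, the date of last contact will be used".

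**The concern.** Whether a stay is counted depends on what happens after it starts. Take two participants who attend the same visit and are admitted on the same later day. One recovers and attends another visit, so the stay is counted. The other dies in hospital with no visit in between, so the stay is not counted. The rule therefore tends to remove the gravest stays, and it can only lower the counts and the days.

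The number of participants discharged is affected too. A terminal stay is one without a discharge, so removing it makes the discharged share of those hospitalised look better.

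The section also sits awkwardly with itself. It provides an end date for fatal stays, which implies that they belong in the table, but its start-date rule excludes most stays that would need that end date.

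**Working it through.** No figure in the plan depends on this rule, so there is nothing to reproduce. The check applies the rule to example dates.

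**Inputs from the documents**

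- Counted if: first IMP < admission < last visit (SAP 11.4).
- Days = discharge − admission + 1 (SAP 11.4), with the imputations above for a missing discharge.
- From Day 43 on, visits fall on Days 43, 71, 99, 127 and 155 (protocol Tables 1-2 and 1-3). They are 28 days apart, with a ±7-day window from Day 71. Two successive visits can thus be 28 + 7 + 7 = 42 days apart, which leaves room for an admission after the last attended visit.

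**Assumed dates** (first IMP on Day 1 throughout)

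| Case | Last visit | Admission | End of stay | Under SAP 11.4 | With the fix below |
|---|---|---|---|---|---|
| 1. Fatal, no visit after admission | 71 | 80 | death 95 | 80 is not before 71: 0 stays, 0 days | 1 stay, 95 − 80 + 1 = 16 days |
| 2. As 1, with an unscheduled visit in hospital | 85 | 80 | death 95 | 80 < 85: 1 stay, 16 days | unchanged |
| 3. Stay leads to withdrawal, EOS visit held | 100 | 80 | discharge 90 | 80 < 100: 1 stay, 90 − 80 + 1 = 11 days | unchanged |
| 4. Stay leads to withdrawal, no later visit | 71 | 80 | discharge 90 | 0 stays, 0 days | 1 stay, 11 days, if discontinuation or last contact is Day 80 or later |
| 5. Admitted on the day of the last visit | 71 | 71 | discharge 75 | strictly, 71 is not before 71: 0 stays, 0 days | 1 stay, 75 − 71 + 1 = 5 days |

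Cases 1 and 2 have the same admission and the same outcome. Only the presence of a study visit during the stay separates them. Case 3 shows that a withdrawal-causing admission is kept when the EOS visit takes place.

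**Imputation.** If the window alone were widened, a non-fatal stay as in case 4 with a missing discharge date would be given the last visit as its end: 71 − 80 + 1 = −8 days. This does not arise today, because such stays are excluded. The imputation date therefore has to change together with the window.

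**Size.** The documents give no rates of hospitalisation, death or missing EOS visits, so the expected number of stays lost cannot be derived and may be zero.

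**The case against.** The strongest case against is that most admissions are unaffected and the serious ones are reported elsewhere.

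- **Withdrawals.** A reader might infer that admissions causing withdrawal drop out in general. The protocol does not support that. Section 4.4 covers early withdrawal and takes each scenario to EOS assessments, Sections 7.1.4 and 7.2 point to it, and a Table 1-2 footnote treats the EOS visit as the withdrawal visit. The stay then precedes the last visit. This objection stands. What remains are participants who never return: Section 7.2 allows consent to be withdrawn at any time, and Section 7.3 covers loss to follow-up. In the latter group the site may not learn of the admission at all.
- **Fatal stays.** A reader might also infer that every fatal stay is lost. Protocol Section 8 allows an unscheduled visit because of an adverse event, and that keeps the stay (case 2).
- **No formal contradiction.** The window acts on start dates and the death rule on end dates, so the two can coexist. That is correct. The death rule still works for a stay that began before the last visit, but it has little else to act on.
- **Comparisons within the SAP.** SAP 8.1 and 4.2.2 serve other purposes and do not set a resource-use window. They show only that the SAP keeps last visit, withdrawal and last contact apart. SAP 11.3 is the closer parallel.
- **SAE data.** The 30-day reporting period in protocol Section 8.3.1 is a safety-reporting duty. This table also covers emergency room visits and starts only after first IMP, so a mismatch with SAE counts is not in itself a defect, and the fix would not remove it.
- **Reporting elsewhere.** Stays are listed, and serious and fatal events are tabulated under SAP 8.2.2. This limits the harm but does not correct the counts and days in the summary.

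**Conclusion.** The point holds in a limited form. For participants with no study visit after admission, chiefly those who die, the final stay is missing from a prespecified table, whereas the same stay is counted in a participant who returns. The direction is certain (downward); the size is unknown. The 16, 11 and 5 days above rest on assumed dates and only show how the rule works. Any percentage understatement would need assumed event counts and should not be attributed to this trial.

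The endpoint is descriptive, and SAP 4.1 and 4.6 plan no testing and no multiplicity adjustment. No primary safety or secondary efficacy result is affected. This is a modest correction, worth making because the rule tends to remove the gravest stays and is easy to repair.

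**What to change.** In SAP 11.4, replace the before-last-visit limit with: started on or before the end of study participation. Define that date as:

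- for completers, and for anyone else with an EOS visit, the EOS/last visit date;
- for participants who end without an EOS visit, the latest of last visit, discontinuation, last contact or death;
- for participants still ongoing at an interim cut, the data cut-off.

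Death should extend the window only where there is no EOS visit. Otherwise a completer who dies after EOS would have later stays counted and a surviving completer would not, which brings back the dependence on outcome.

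Use the same date in place of the last visit date when imputing a missing discharge for a non-fatal stay, so that durations cannot be negative. The death-date rule for fatal stays can remain.

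The cost is a short text change and a small programming change. The hospitalisation figures may become slightly less favourable.

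### SAP 11.4 fills a completely missing discharge date with no upper limit and no check against later visits, so one hospital stay can be counted as months or years

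*SAP*

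**What the plan says.** SAP Section 11.4 summarizes hospital stays and ER visits together, with one duration formula: "Total number of days in hospitalization/ ER visit for each hospitalization/ER visit= Discharge date – hospitalization/ ER visit date +1". Durations are then added up by cycle ("Total number of days in hospitalization/ ER visit for each cycle = sum of total number of days") and over cycles for the whole study. Results are descriptive, by study, cycle, dose received in the cycle, and overall.

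The imputation is introduced with "In case of completely missing discharge date, the following imputation rules will be applied for the discharge date". Three routes follow:

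- a later stay exists: "Hospital start date of next hospital stay – 1 as end date of this hospital stay";
- the participant died: "Death date in case participant died and the end date of hospital stay is missing";
- the participant did not die: "Last visit date if the end date of hospital stay is missing and the participant did not die".

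A date with only the day missing is handled more tightly: "In case that discharge date is partially missing (day missing) then impute to last day of the month", or earlier if the next admission or death intervenes. On which events count, the section says: "Only hospitalization started after first IMP and before last visit will be considered in the summary".

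The section sets no maximum length, does not compare the imputed date with visits the participant attended, and plans no summary without imputed stays. Duration of hospitalization is listed in Protocol Section 3 under the Other objectives and again in SAP Section 2.2.6.

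**The concern.** A missing discharge date says nothing about when the participant left hospital. The rule nevertheless treats the participant as an inpatient until the next admission, death or the last study visit. The imputed length therefore depends on how long the participant was followed, not on the illness.

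The trial's own data can often contradict it. The schedules in Protocol Section 1.3 have weekly dosing visits at site or at home during each cycle, then Observation Period visits, then site visits every 12 weeks when no treatment is given. A participant counted as hospitalized throughout could have attended many of these and received further cycles.

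The SAP is more careful with similar problems. In Section 11.4 itself, a date lacking only the day is held to the month end. In Table 4–1, an adverse event duration that rests on an imputed date is reported as a bound. Here the imputed length enters the summaries as if it had been observed.

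At stake are the total, mean, SD and maximum of hospital days, overall and by cycle and dose.

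**Working it through.** The documents give no expected number of hospital days and no count of missing discharge dates, so there is no figure of the plan to reproduce. The check applies the SAP's formula to its own imputed dates.

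**Inputs from the documents**
- Length = discharge − start + 1, and the three routes (SAP 11.4).
- Follow-up categories at 360, 720 and 1080 days, the last open-ended (SAP 8.1); end of the Observation Period at Day 155 (SAP 3.2.2).
- Follow-up runs until product approval or a managed access program (Protocol 4.1), but 14 months in Denmark and the UK (Protocol 10.8).
- Continuous variables: n, mean, SD, median, minimum, maximum (SAP 3.1).

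**Assumed:** the start days, and the number and length of the other stays.

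**Step 1, last-visit route, start on Day 60**
- Last visit Day 155: 155 − 60 + 1 = 96 days
- Day 360: 360 − 60 + 1 = 301 days
- Day 720: 720 − 60 + 1 = 661 days
- Day 1080: 1080 − 60 + 1 = 1021 days
- 14 months at the SAP's 30 days per month, Day 420: 420 − 60 + 1 = 361 days

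**Step 2, next-stay route, start on Day 30**
- Next stay Day 120: 119 − 30 + 1 = 90 days
- Day 395: 394 − 30 + 1 = 365 days
- Day 730: 729 − 30 + 1 = 700 days

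The death-date route has the same form when death comes long after the stay.

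**Step 3, weight of one record.** Assume 20 other stays of 7 days (140 days) and one stay that truly lasted 1 day, so the true total is 141 days.

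| Imputed length | Total | Share of total | Total ÷ 141 |
|---|---|---|---|
| 301 | 441 | 301/441 = 68% | 3.1 |
| 661 | 801 | 661/801 = 83% | 5.7 |
| 1021 | 1161 | 1021/1161 = 88% | 8.2 |

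With the 1021-day record, the mean per stay goes from 141/21 = 6.7 to 1161/21 = 55.3 days. The median of the 21 stays is 7 days either way.

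**Step 4, range over case mix**
- 10 other stays of 3 days: 1021/(30 + 1021) = 97%; 301/(30 + 301) = 91%.
- 80 other stays of 14 days: 1021/(1120 + 1021) = 48%; 301/(1120 + 301) = 21%.

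For imputed lengths of 301 to 1021 days the share thus runs from 21% to 97%. A shorter record weighs less: 96 days against the heaviest mix is 96/(1120 + 96) = 8%.

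**The case against.** Several points count against giving this much weight.

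- **Rank.** The endpoint falls under the Other objectives, nothing is tested (SAP 4.1, 4.6), and the median is robust. This stands.
- **Frequency.** Inpatient hospitalization makes an adverse event serious (Protocol 10.3), and serious events are reported promptly and followed to resolution or stabilization (Protocol 8.3). That makes sites follow these events, so missing discharge dates may be few. It does not guarantee a discharge date, and one missing date is enough for the effect shown.
- **Visibility.** The maximum would expose an extreme value. Under the general date rule in SAP 4.2.2, listings show dates as reported, so a blank would be seen. That helps a careful reader but does not correct the table.
- **The rule is sometimes right.** For a participant still in hospital at the last visit, the last visit date is reasonable. The SAP does not limit the rule to that case.

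A reader might also infer more than the text supports:

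- **That an ER visit will certainly be turned into a stay of years.** All three imputation bullets speak of a hospital stay. Extending them to ER visits follows only from the shared duration formula, and the SAP does not settle it.
- **That all imputed days go to the cycle of admission.** The section refers to events within the cycle and gives no rule for a stay that crosses cycles.
- **That a particular multiple, such as 8-fold, is the expected distortion.** It belongs to one assumed case mix.

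**Conclusion.** The point holds for hospital stays. Followed as written, SAP 11.4 can turn a short stay with no discharge date into one of months or years, even where attended visits show that the participant had left hospital. This is a rule that gives a wrong value, not merely a missing detail.

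One imputed record of 301 to 1021 days makes up 21% to 97% of all hospital days for between 10 stays of 3 days and 80 stays of 14 days. Those case mixes and the start days are assumptions, and the number of missing discharge dates is unknown, so the actual effect cannot be stated. It could be nil. The damage is confined to the total, mean, SD and maximum of one descriptive endpoint; no primary safety or secondary efficacy result is affected. For ER visits and for allocation to cycles, the supportable statement is that the SAP is unclear.

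**What to change.** In SAP Section 11.4:

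1. Make observed durations the main summary, and report the number of stays with a missing discharge date.
2. Where a duration is imputed, end it at the earliest of the day before the next attended outpatient site or home visit, the day before the next stay, and death. Use the last visit date only if no attended outpatient visit follows the admission. Virtual visits should not count, because they do not show that the participant was out of hospital.
3. Show totals with and without imputed stays.
4. State that ER visits without admission are outside the hospital-stay imputation and count as one day.
5. State how a stay that crosses cycles is assigned.

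The cap limits the error but does not remove it: with site visits every 12 weeks, an imputed stay could still run to about 12 × 7 = 84 days, plus the visit windows, or longer if visits are missed. That is why observed durations should lead.

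An adverse event end date should not stand in for discharge. Neither document describes a link between the two records, and an event can resolve before discharge or persist after it.

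The cost is SAP wording and a somewhat longer derivation from scheduled-visit dates. Some durations will remain missing in the main summary.
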